Proton pump inhibitors (PPIs), widely used to reduce gastric acid, inhibit the proton-47 potassium ATPase in parietal cells at the final step in gastric acid secretion, thereby reducing 48 49 gastric acidity [17]. Lower gastric acidity may be insufficient to solubilize dietary iron, interfere with intestinal iron absorption and potentially induce iron deficiency [18, 19]. Previous studies 50 have demonstrated the use of PPIs, including pantoprazole and esomeprazole, in managing iron 51 overload in thalassemia patients and observed a reduction in systemic iron accumulation [20-23]. 52 Additionally, dietary factors such as calcium-rich foods and polyphenols can reduce iron 53 absorption [24]. Resveratrol that is an antioxidative polyphenolic compound [25, 26] can reduce 54 oxidative stress, improve hepatic iron-overload states [27, 28], decrease intestinal iron absorption 55 56 [29] and increase fetal hemoglobin (HbF) levels in beta-thalassemia patients [30].

57 Nowadays, the standard treatment for iron overload in thalassemia involves iron chelation 58 therapy which standard iron chelators including deferasirox (DFX), deferiprone (DFP) and 59 deferoxamine (DFO) are used in Thailand. However, parenteral administration of DFO, limited accessibility to DFX, and severe side effects or suboptimal outcomes with DFP may hinder effective management in NTDT patients with iron overload. Given these limitations and the underlying mechanisms of iron overload, this study aims to investigate the effects of omeprazole as PPI and resveratrol as an adjuvant on dietary iron absorption in NTDT patients. We hypothesize that these interventions could further reduce systemic iron levels through their proposed mechanisms.

66

67 **Research Hypothesis**

68 69

70 71 Adjunctive omeprazole or resveratrol in combination with iron chelators could reduce serum ferritin compared with placebo.

- 72 Study Goals and Objectives
- 73

77

74 Primary Objective

To evaluate the efficacy of adjunct omeprazole or resveratrol in combination with iron
 chelators in reducing serum ferritin compared to placebo

- 78 Secondary Objectives
- 1. To evaluate the efficacy of adjunct omeprazole or resveratrol in combination with iron
 chelators in reducing labile plasma iron (LPI), non-transferrin bound iron (NTBI) and serum iron
 (SI) compared to placebo

2. To study the association between adjunct omeprazole or resveratrol in combination with
 iron chelators and the levels of ERFE and hepcidin (Hcd)

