
- 3. To study the association between resveratrol and changes in HbF levels
- 84 85
- 4. To assess the adverse effects of adjunct omeprazole or resveratrol with iron chelators
- 86

87 Ethics

88 This study has been approved by the Human Experimentation Committee Research Institute for Health Sciences and authorized by Associate [name], Ph.D., a 89 90 Chairman of the Committee, Faculty of Medicine, Chiang Mai University, Chiang Mai 50200, Thailand, Certificate Number: 476/2024 (English version) and 476/2567 (Thai version), Date: 17th 91 92 December 2024. Adherence to ethical guidelines was of prime importance throughout the study process. All patients will be fully informed about the particulars of the study and willingly provide 93 94 their signatures on the consent forms before any study procedures are performed. This study 95 follows the guidelines of the Helsinki Declaration 2008, revised in 2013: Ethical Principles for Medical Research Involving Human Subjects. Subjects' rights have been protected by an 96 appropriate Institutional Review Board and written informed consent will be granted from all 97 98 subjects.

99

100 Methods

- 101
- 102 Study Design
- 103 Phase 3, randomized, double-blind, placebo-controlled trial
- 104

105 Scope of Research

Non-transfusion thalassemia patients with secondary iron overload visiting Out-patient
 department numbers 9 or 23 at the Division of Hematology, Department of Internal Medicine,
 Faculty of Medicine, Chiang Mai University, Chiang Mai, Thailand between 10th February 2025
 and 30th April 2026.

110 111

Study Population

112

113 Inclusion Criteria

- 114 Age 20-65 years
- 115 Non-transfusion dependent thalassemia [alpha or beta] diagnosis by HPLC, PCR or gene 116 mutation
- Hemochromatosis with serum ferritin 300-1000 ng/mL or > 1000 ng/mL with maximum
 iron chelator (DFP at 75 mg/kg/day or DFX at 20 mg/kg/day)
- Concurrent iron chelators without changing dose during 3 months before enrollment and
 no tendency to adjust the dose of iron chelators between study
- 121 Inform consent
- 122

123 Exclusion Criteria

- 124 Pregnancy or breastfeeding
- Chronic inflammation or other conditions that might confound serum ferritin
 interpretation
- Alanine transaminase more than 5 times upper limited of normal, creatinine clearance < 60 mL/min
- 129 Can not receive oral medication
- 130 Currently receive omeprazole or resveratrol
- 131 allergy to omeprazole or resveratrol
- 132

133 Discontinuation Criteria

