- Have more or equal than grade 3 adverse events
- 135 Have conditions that are not suitable for continuation of study
- 136 Protocol violations that significantly affect data collection or interpretation
- 137 Pregnancy
- 138 Need to increase the dose of iron chelation while currently in study
- 139 Have indication for proton pump inhibitor or resveratrol such as gastrointestinal bleeding
- 140 Withdrawal of informed consent
- 141
- 142 Sample Size Calculation
- Expected standardized difference of 0.22 from the Eghbali et al. [22] study which found that adjunct pantoprazole with iron chelators could lower serum ferritin more than iron chelators alone by decreasing serum ferritin from 1444 ± 613 ng/mL to 1197 ± 956 ng/mL and 1928 ± 694 ng/mL to 1501 ± 385 ng/mL respectively. If alpha = 0.05 and beta = 0.2, the estimated sample size is 20 persons in each study group [31] as shown in Table 1.
- **Table 1** Estimated stepped rules of thumb for required trial sample size/treatment arm [31].

Standard difference	80% powered main trial	90% powered main trial
Extra small ($\delta < 0.1$)	50	75
Small $(0.1 \le \delta < 0.3)$	20	25
Medium $(0.3 \le \delta < 0.7)$	10	15
Large ($\delta \ge 0.7$)	10	10

149

150 Study Intervention

- Divide the patients into three study groups in a 1:1:1 ratio using stratified randomization
 based on gender (male and female) and serum ferritin (<1,000, equal to 1,000 or >1,000
 ng/mL). The randomization will be used web-based randomization.
- Allocation concealment will use sealed envelopes to ensure concealment, A staff member not involved in this study will place the study drugs into opaque, sealed envelopes and label them into unique codes. The patients will receive the study drug corresponding to the code on their envelope, without knowing the content. The code lists will be securely stored and remain inaccessible to the research team during the trial.
- This study will use a double-blind technique for patients and outcome assessors. Three study compounds including omeprazole, resveratrol and placebo will be prepared and filled in gelatin capsules with the same appearance as follows; 20 mg omeprazole capsule, 250 mg resveratrol capsule and 20 mg maltodextrin. The capsules will be packed in a white plastic bottle (30 capsules each) and labeled codes under the bottles.
- The patients in Group 1 will take an omeprazole capsule orally twice daily (total 40 mg/day) in the morning and evening before meal for 6 months.

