- The patients in Group 2 will take a resveratrol capsule orally twice daily (total 500 mg/day)
 in the morning and evening before meal for 6 months.
- The patients in Group 3 will take a placebo capsule orally twice daily in the morning and evening before meal for 6 months.
- All groups will receive standard treatments including iron chelators, folic acid
 supplementation, vitamin D supplementation, calcium supplementation and lifestyle
 modifications throughout the study.

Research Design

 - The patients will be appointed at the first visit, 3 months and 6 months to evaluate clinical signs, blood parameters and side-effects. If there are side effects more or equal to grade 3, the doctors may decrease the dosage of the study drug according to the following table.

	Side effects	Dose	adjustmen	t	
	Grade \geq 3 Nausea, vomiting, diarrhea, bloating	Decreased study drug 1 lev daily dose]	vel [from tw	vice daily do	ose to once
3	- In each visit, the patients will be requested to collect their blood (30 mL) which will be				hich will be
)	separated into EDTA-whole blood (5 mL) and clotted blood (25 mL). Whole blood will be				
)	used for complete blood count (CBC) analysis and Hb typing. Clotted blood will be				
	separated into the serum to be used for quantitation of kidney function biomarkers such as				kers such as
2	blood urea nitrogen (BUN) and creatinine (Cr); electrolytes (e.g., Na ⁺ , K ⁺ , Ca ²⁺ , Mg ²⁺ and			$^{2+}$, Mg ²⁺ and	
3	phosphates); liver function biomarkers such as aspartate aminotransferase (AST), alanine				
ŀ	aminotransferase (ALT) and alkaline phosphatase (ALP); and iron parameters such as				
5	serum ferritin (sFt, SI), total iron-binding capacity (TIBC), NTBI, LPI, Hcd and ERFE			l and ERFE	
6	according to the below table.				
			at at 14	and	and

Activities	1 st visit	2 nd visit	3 rd visit
History taking and physical examination			

Blood for CBC, BUN, Cr, electrolytes, AST, ALT, ALP, sFt, %TS, TIBC, SI, Hb typing, LPI, NTBI, Hcd and ERFE		
Blood for quantitation of serum vitamin B12, vitamin D, Ca^{2+} and Mg^{2+} , and determination of Hb type		
Adverse effect record		

187

188 Laboratory Investigation

- 1) CBC will be analyzed using an automated Beckman Cell Analyzer machine according to the
 manufacturer's instruction at the Central Laboratory, Maharaj Nakorn Chiang Mai Hospital,
 Faculty of Medicine, Chiang Mai University.

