- 192 2) Hb typing will be performed at the Hematology laboratory, Department of Internal Medicine,193 Chiang Mai University.
- 3) Serum BUN, Cr, electrolytes, AST, ALT, ALP, sFt, SI and TIBC will be quantified using an
 automated Roche Cobus Biochemical Analyzer machine according to the manufacturer's
 instruction at the Central Laboratory, Maharaj Nakorn Chiang Mai Hospital, Faculty of
 Medicine, Chiang Mai University.
- 4) Serum iron parameters will be quantified at the Oxidative Stress Laboratory, Department of
 Biochemistry, Faculty of Medicine, Chiang Mai University using specific reagents and
 techniques as described below.
- 4.1) LPI using rhodamine B fluorescence probe [32]
- 4.2) NTBI using NTA chelation/iron chelator fluorescence beads/flow cytometry [32]
- 4.3) Hcd using a sandwich ELISA kit (ABBEXA limited company, Cambridge, UK)
 according to the manufacturer's instruction [33]
- 4.4) ERFE using a sandwich ELISA kit (ABBEXA limited company, Cambridge, UK)
 according to the manufacturer's instruction [34]

208 Statistical Analysis

207

All patients who receive at least 1-time study drug will be analyzed in an Intention-to-treat 209 210 analysis. Patients who receive at least 80% of the study drug will be analyzed in a Per-protocol analysis. Descriptive statistics will be used for the analysis of demographic data. Primary outcome 211 and secondary outcomes [continuous variable] will be analyzed using Friedman's analysis of 212 variance (ANOVA) test. Secondary outcomes [dichotomous variable] will be analyzed using Chi-213 square or Fisher exact test for independent data or Cochran's Q test for dependent data. The 214 association between continuous variables will be analyzed using Pearson's or Spearman's test. 215 216 Accordingly, a P-value <0.05 is considered statistical significance.

217 Duration of Study Plan

```
219
```

References 220

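### Friedman's test, the only test named for the primary and continuous secondary outcomes, compares visits within patients, so the stated method does not test the comparison with placebo

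*Protocol*

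**What the plan says.** The question is a comparison of arms. The Primary Objective is the efficacy of either adjunct added to iron "chelators in reducing serum ferritin compared to placebo". The first Secondary Objective asks the same of LPI, NTBI and serum iron.

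The design is parallel. Study Design reads "Phase 3, randomized, double-blind, placebo-controlled trial". Study Intervention says: "Divide the patients into three study groups in a 1:1:1 ratio using stratified randomization". Each group takes one compound for 6 months; for example, "The patients in Group 3 will take a placebo capsule orally twice daily in the morning and" evening. No crossover and no matched triplets are described. Under Research Design, "The patients will be appointed at the first visit, 3 months and 6 months to evaluate clinical" signs, blood parameters and side effects, so each patient has three measurements.

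Statistical Analysis then says that the primary outcome "and secondary outcomes [continuous variable] will be analyzed using Friedman's analysis of" variance. For dichotomous secondary outcomes the same section gives chi-square or Fisher tests for independent data and Cochran's Q for dependent data. For continuous outcomes it gives only the dependent-data test. It adds that the "association between continuous variables will be analyzed using Pearson's or Spearman's test".

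**The concern.** Friedman's test needs related measurements in blocks. In this trial the patient is the only natural block and visit is the only repeated factor. The test can say whether ferritin changed over the three visits. It cannot say whether it changed more on omeprazole or resveratrol than on placebo.

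The risk is that a background change is credited to the drug. Study Intervention states: "All groups will receive standard treatments including iron chelators, folic acid" and other supplements, with lifestyle modification. A fall shared by all arms is therefore possible. Friedman's test would register that fall in an active arm whether or not the study drug contributed. In the other direction, a real difference between arms can leave the pooled test unmoved.

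**Working it through.** The plan prints no figure on this point, so there is none to reproduce. The 20 patients per arm are taken from Sample Size Calculation as given; whether 20 is adequate is a separate matter.

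**Step 1: what the statistic uses.** With n patients and k visits, values are ranked within each patient and R_j is the rank sum at visit j:

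Q = 12 / [n k (k+1)] × Σ R_j² − 3 n (k+1)

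With k = 3, 12 / (n × 3 × 4) = 1/n and 3n × 4 = 12n, so Q = (1/n) Σ R_j² − 12n, referred to chi-square with 2 df. No term carries the arm. As a check, 60 simulated patients with 3 visits gave Q = 0.30, p = 0.861. After the patients were shuffled across arm positions, the result was identical.

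**Step 2: Friedman against a between-arm test.** There were 4,000 simulated trials per setting, with 20 per arm and 3 visits. Normal data, SD 1, correlation 0.7 between visits and linear change over the visits are assumptions, not document figures. The between-arm test is Kruskal-Wallis on the 6-month change.

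| Setting | Friedman, pooled | Friedman, each arm | Between-arm test |
|---|---|---|---|
| No arm difference, all fall 0.5 SD | 97% | 55–57% (placebo included) | 4.7% |
| Arms change by −0.8, 0 and +0.8 SD | 2% | 93%, 5%, 92% | about 100% |

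Pooled Friedman rejects when the arms are alike and is silent when they differ strongly.

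**Step 3: how often a shared fall gives a significant result in a given arm.** The scale comes from the study quoted in Sample Size Calculation: (1444 − 1197)/613 = 247/613 = 0.40 SD and (1928 − 1501)/694 = 427/694 = 0.62 SD. Assumptions: no drug effect, normal data, equal SDs, linear shared fall, 20 per arm, within-patient correlation 0.5–0.8.

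- Fall of 0.4 SD: Friedman gives p < 0.05 in a given arm in about 25–54% of trials.
- Fall of 0.6 SD: about 50–88%.

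**Step 4: a decision rule that the protocol does not state.** Suppose significance in at least one active arm, without significance in placebo, were read as efficacy. Under the assumptions of step 3 this occurs in about 33–38% of trials (0.4 SD) and 12–38% (0.6 SD).

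**Step 5: sensitivity to the SDs.** The quoted SDs are not constant (613 to 956, and 694 to 385). Using them, with the month-3 SD interpolated, step 3 becomes about 16–28% for the 0.40 SD fall and 67–92% for the 0.62 SD fall. The direction holds, but the exact range does not.

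**The case against.** The strongest general defence is that a statistical analysis plan, not shown, may name a between-arm test. It may, but the protocol is not silent here. It fixes a specific test for its primary outcome, and that test does not address the objective. A later plan naming another method would depart from the protocol. The randomisation strata could in principle serve as Friedman blocks, but the protocol does not propose this, and strata are not matched triplets.

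Several stronger readings are tempting, and the documents do not support them.

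- *Ferritin must be expected to fall in every arm.* Inclusion Criteria require a chelator dose unchanged for 3 months and unlikely to be adjusted in the study. A shared fall is possible, not established.
- *The cited study shows the size of that background fall.* Read literally, 0.40 SD is the pantoprazole arm's own change, and only 0.62 SD comes from chelators alone. By its title that study covered thalassemia major and intermedia. The figures serve only as a scale.
- *The plan has a 12–38% false-positive rate.* Statistical Analysis does not say whether Friedman is run per arm or pooled, nor how a within-arm result would be interpreted. The figure applies only under the rule assumed in step 4. With no change over time that rule still fires in about 10% of trials, but this mostly reflects two chances at 0.05: two valid unadjusted Wilcoxon contrasts gave 9.4%. It is no evidence against Friedman.
- *Randomisation and the placebo arm are wasted.* The data would still support a proper comparison.
- *No outcome is compared between arms.* Dichotomous secondary outcomes do have independent-group tests.
- *The correlation sentence is a second defect.* It is not assigned to the objectives on ERFE, hepcidin and HbF. As continuous secondary outcomes, these already fall under the Friedman sentence.

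**Conclusion.** The point stands as an error in the stated method. Friedman's test is the only analysis named for the primary and continuous secondary outcomes. In this parallel design it assesses change over visits and does not use arm membership. The comparison of ferritin, LPI, NTBI and serum iron with placebo is therefore not tested by the method the protocol names. This follows from the form of the statistic and needs no simulation.

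The size is illustrative. Under the assumptions of step 3, a fall shared by all arms gives a significant Friedman result in a given arm in about 25–88% of trials with no drug effect, and the range moves if SDs differ between visits. The 12–38% figure depends in addition on a reading of the results that the protocol does not state. It should be corrected before analysis because it concerns the primary hypothesis.

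**What to change.** Replace the Friedman sentence in Statistical Analysis with a between-arm analysis of month-6 serum ferritin, on the log scale if skewed. Either ANCOVA at month 6 or a mixed model for months 3 and 6 would serve, with arm as a factor and adjustment for baseline ferritin and the stratification factors (gender and ferritin category).

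Report two planned contrasts, omeprazole minus placebo and resveratrol minus placebo, each with a 95% confidence interval, and state a multiplicity rule such as Holm. A rank-based between-arm test on change from baseline is an acceptable alternative.

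Use the same approach for LPI, NTBI, serum iron, ERFE, hepcidin and HbF. Keep Friedman's test, if wanted, only as a description of change within each arm.

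The cost is wording only, with no new visits or data. The multiplicity rule makes the test slightly stricter: under Holm the smaller of the two p-values is judged against 0.05/2 = 0.025.

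### Secondary objectives 2 and 3 (ERFE, hepcidin, HbF) name no placebo comparator, and neither stated method for these continuous outcomes compares the arms

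*Protocol*

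**What the plan says.** **Objectives.** The primary objective sets the two adjuncts against placebo for serum ferritin. Secondary objective 1 (LPI, NTBI, serum iron) does the same and closes with "SI) compared to placebo". The next two objectives change form:

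- Secondary objective 2: "To study the association between adjunct omeprazole or resveratrol in combination with" "iron chelators and the levels of ERFE and hepcidin (Hcd").
- Secondary objective 3: "To study the association between resveratrol and changes in HbF levels".

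Neither mentions placebo.

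**Methods.** Three sentences in the protocol's Statistical Analysis section could bear on these outcomes:

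- "secondary outcomes [continuous variable] will be analyzed using Friedman's analysis of" variance. ERFE, hepcidin and HbF are continuous, so this sentence covers them.
- Dichotomous secondary outcomes get Chi-"square or Fisher exact test for independent data or Cochran's Q test for dependent data".
- The "association between continuous variables will be analyzed using" Pearson's or Spearman's test.

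**Design.** Study Design and Study Intervention describe a double-blind trial with three arms (omeprazole, resveratrol, placebo) randomised 1:1:1. Research Design sets visits at entry, 3 months and 6 months. Its text has blood drawn at every visit, with Hb typing, hepcidin and ERFE among the tests.

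**The concern.** ERFE and hepcidin bear on how the drugs might act on iron absorption, and the protocol's introduction cites HbF as a possible benefit of resveratrol. The trial has a randomised placebo arm that can answer whether either drug changes these markers. For that, the objective should name the contrast with placebo and the analysis should contain it. In the text as it stands, neither does.

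Without the contrast, a change in HbF during six months on resveratrol could be reported as an effect of resveratrol when the placebo arm changed just as much. In the other direction, a real effect could be missed if it offsets a drift that all arms share.

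**Working it through.** The protocol states no figure for this point. The check is therefore one of text and method, followed by an illustration of size.

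**Step 1. Match each stated method to the question.** The question is whether change in a marker differs between a drug arm and placebo.

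| Stated method | Scope in the protocol | Applies to ERFE, hepcidin, HbF? | Contains study arm? |
|---|---|---|---|
| Friedman's test | Primary outcome and continuous secondary outcomes | Yes | No: over three visits, the patient is the block and the visit is the factor |
| Chi-square or Fisher | Dichotomous secondary outcomes, independent data | No | Could, but out of scope |
| Cochran's Q | Dichotomous secondary outcomes, dependent data | No | No |
| Pearson or Spearman | Pairs of continuous variables | Only marker with marker | No: arm is a three-level nominal variable |

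Friedman's test cannot be turned round so that the arms are its factor. Each block would then need a value from every arm, and each patient here is in one arm only.

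**Step 2. What a within-arm test sees.** Let T be the change from entry to month 6 that would occur in every arm, and E the added effect of the drug.

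- Expected change in the drug arm: T + E
- Expected change in the placebo arm: T
- Difference between arms: (T + E) − T = E

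A test of visits within the drug arm responds to T + E. Only the difference between arms isolates E.

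**Step 3. Illustration of size.** From the protocol: three arms, 20 patients per arm (Sample Size Calculation), three visits, significance level 0.05. Assumed, not in the protocol: marker SD 1, correlation 0.7 between any two visits of one patient, T and E building up linearly over the visits, E present in the resveratrol arm only, normal data, two-sided tests, no dropout. There were 3,000 simulated trials per row, so the Monte Carlo standard error is at most about 0.9 percentage points. The entries are the percentage of trials with P < 0.05.

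| T (SD) | E (SD) | Friedman, resveratrol arm | Friedman, all arms pooled | Pearson: change with an unrelated variable | Change, resveratrol vs placebo (t-test) |
|---|---|---|---|---|---|
| 0 | 0 | 5.6 | 5.4 | 5.1 | 4.7 |
| 0.8 | 0 | 93.1 | 100 | 5.2 | 5.2 |
| 0 | 0.8 | 92.8 | 40.7 | 5.3 | 88.9 |
| −0.8 | 0.8 | 4.6 | 97.5 | 5.2 | 89.7 |

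Hand check of the last column: the variance of a change is 2 × (1 − 0.7) = 0.6. The standard error of the difference between arms is √(0.6 × 2/20) = 0.245, and 0.8/0.245 = 3.27. By the normal approximation, power is Φ(3.27 − 1.96) = Φ(1.31), about 90%, in line with the simulated values.

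**Reading the table.** In row 2 the drug does nothing, yet Friedman's test within the arm rejects in 93% of trials. In row 4 the drug works and that test rejects in about 5%. The between-arm comparison stays near 5% when E = 0 and near 90% when E = 0.8, whatever T is. The Pearson column is flat by construction. It shows only that correlating change with a variable unrelated to arm carries no information on E.

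**The case against.** **Objectives 2 and 3 do have a method.** Friedman's test is assigned to continuous secondary outcomes, so correlation is not the only analysis on offer. This stands. A reader who goes from the word association to the correlation sentence might infer that these objectives are meant to be answered by correlation. The protocol makes no such link. The point survives because Friedman's test has no arm term either.

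**The Friedman problem is wider than these two objectives.** It applies equally to ferritin and to secondary objective 1, both of which do name placebo. This also stands. Correcting the method for all continuous outcomes would cover ERFE, hepcidin and HbF as well. What is particular to objectives 2 and 3 is that their wording lacks the comparator, so such a correction would not clearly reach them.

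**In a randomised trial, association with a drug can mean association with assigned arm.** That is a fair reading, and the protocol nowhere says that placebo will be ignored. But none of the tests it names for continuous outcomes would carry that reading out.

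**Arm could be coded 0/1 in a Pearson correlation.** With two arms this is equivalent to a two-sample t-test, so it is not mathematically impossible. The protocol, however, limits the method to continuous variables and describes no such coding.

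**Inflated type I error from correlating repeated visits.** A reader might infer that all visits and arms will be pooled in the correlations, with P-values too small or correlations created by treatment shifts. The protocol describes no such pooling and does not use a marker-to-marker correlation to answer an objective. No error rate can be attached to the plan on that ground.

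**The SAP may add the contrast.** It may, and leaving detail to it is normal. But the protocol has already fixed objectives without a comparator and named tests that do not compare arms, so an SAP that did so would depart from both.

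**Conclusion.** The point holds as a mismatch between two secondary objectives and the methods named for them. Objectives 2 and 3 state no comparator. Of the two methods that could apply to ERFE, hepcidin and HbF, correlation is limited to pairs of continuous variables and Friedman's test over visits compares patients with themselves. On either, the placebo arm plays no part, and a drug effect cannot be separated from a trend common to all arms.

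This conclusion rests on the text and on one reading: that Friedman's test is applied over the three visits, the only repeated factor in the design. The percentages rest on the assumed trend, effect and within-patient correlation. With no common trend, the within-arm test keeps its nominal level (5.6% in the simulation); at 0.8 SD it rejects in 93%. The documents do not say where in that range, or beyond it, the true trend lies. The outcomes are secondary, so this should be corrected but does not by itself threaten the primary question.

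**What to change.** 1. Reword objective 2 as the effect of each adjunct, compared with placebo, on change from baseline to month 6 in ERFE and hepcidin. Reword objective 3 as the effect of resveratrol, compared with placebo, on change in HbF over the same period.
2. Name a between-arm analysis that gives an estimate with a 95% CI: for example ANCOVA adjusted for the baseline value, a mixed model with arm and visit, or a rank-based equivalent if the distributions call for it. Use the same approach as in any correction of Friedman's test for ferritin and the other continuous outcomes.
3. Keep Pearson's and Spearman's tests for description only, with one value per patient, and state that they answer no objective.

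The cost is the wording of two objectives and of the analysis sentences. By the Research Design text, these tests are already drawn in every arm at each visit (assuming HbF is read from the Hb typing), so no new data are needed.
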